The protocol implemented by Sella, F. et al. (2023) is followed, with the 40 meters sprint being the first test. Prior to performing the sprints, participants completed a 10-minute standardized warm-up comprising jogging, dynamic stretches, running drills, and three stride-outs at increasing intensity. The physical tests are then performed, beginning with a 40-meter sprint. After an adequate 10-minute rest period, the Bronco test is performed. After 20 minutes, strength tests are performed, starting with the squat and then the bench press, and ending with the Borg scale.

This protocol is followed on both testing days; participants perform tests on the same day of the following week, at the same time

- **Background**

Specifically, in the case of nitrates in rugby, the evidence is scarce. There are some studies, such as the one conducted by Esen et al. (2023), which evaluated the effect of beetroot supplementation on trained male rugby players. They were given an average of 12.8 mmol of nitrates and a placebo with less than 0.08 mmol of nitrates, ingested 3 hours before physical tests. These studies revealed no improvement in the yo-yo endurance test or the countermovement jump.

On the other hand, there is the study conducted by López-Samanes et al. (2022) on semi-professional female rugby players, which studied the influence of beetroot on neuromuscular performance. Providing similar amounts of nitrates to the aforementioned study yielded a positive response in the countermovement jump exercise; however, there were no differences in speed, agility, strength, and endurance tests. Thus, despite the dose, differences are found depending on the protocol used.

However, while specific studies on rugby are limited, there is research in sports or activities with similar characteristics. An example of this is the study by Domínguez et al. (2018), who evaluated the effect of beetroot supplementation on high-intensity intermittent exercise. Their research observed an improvement in performance when rest periods between efforts were short. These improvements were primarily attributed to increased resynthesis of phosphocreatine, which contributes to delaying its depletion. Increases in muscle power and speed were also reported, as well as a possible reduction in muscle fatigue, although the specific physiological pathway through which this response occurs is not yet fully understood.

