In his study, Fernandes (2021) conducted a literature search on nutritional supplements that improve performance in elite soccer players, revealing the use of various supplements such as creatine, caffeine, sodium bicarbonate, beta-alanine, nitrates (from beetroot), among others. The results, focused on nitrates, reveal that 6 mmol of NO₃, used for at least 5 days, consumed 2 hours before training, improves soccer players' performance. Furthermore, they emphasize the importance of doubling the dose on game day. This study, compared to those presented initially,

highlights the need to find an appropriate protocol, including dosage and application time, for each specific sport. Although the trend for ball sports, according to these studies, implies the need for chronic, not just acute, intake, reflecting the need for further research in the field.

Delleli et al. (2023) conducted a systematic review of randomized controlled clinical trials evaluating the effect of beetroot supplementation on combat sports performance. They concluded that there was an improvement in different aspects of athletic performance, both with a single supplementation and multiple doses, in different combat sports; mainly oxidative metabolism in isometric and isokinetic exercises; however, there is variability in the results, associated with both individual factors and the characteristics of each individual sport. There are also other systematic reviews (Murphy et al. 2022 and Tan et al. 2022) that reflect the study of nitrates in sports, including team sports, with variability in their results. Therefore, the need for further research on the subject is evident, mainly in Colombia, where no results on the study of nitrates in rugby are found.

In addition, this supplement is endorsed by the Australian Institute of Sport (AIS) for use by classifying it in category A, due to its safety and level of scientific evidence (2022).

- Human subjects protection review board

Initially, the study was considered experimental and approved by the committee of the Faculty of Medicine of the National University of Colombia in minutes B.FM. 1. 002-CE-043-24. However, as the necessary sample of volunteers for randomization was not obtained (44 people were required, but 10 were obtained), the study was changed from experimental to quasi-experimental, and the changes were reviewed and approved by the same committee in minutes 2.FM. 1. 002- CE 105-25.

Bibliographic references:

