A descriptive and exploratory analysis was performed on the collected data using the R program. Univariate tests were performed for the mean (paired Student t-test) or Wilcoxon depending on the type of variable (continuous or ordinal) and compliance with the assumptions of normality with a confidence level of 95%.

$$d = \frac{\bar{d}}{s_d}$$

Where:

\bar{d} = mean of the differences (Beetroot – Placebo)

s_d = standard deviation of the differences

Thus, for the Wilcoxon test, the following was used:

$$r = \frac{Z}{\sqrt{n}}$$

Where:

Z = Z statistics of the test

n = number of participants with data in both conditions

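### No interval is named for d or r, d has no small-sample factor, and a continuous outcome judged non-normal is reported only as r (low priority, cheap improvement)

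*Combined protocol and SAP*

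**What the plan says.** The Statistical Analysis Plan (SAP) opens by describing its purpose: "A descriptive and exploratory analysis was performed on the collected data using the R program". It then offers a paired t-test or a Wilcoxon test, chosen "depending on the type of variable (continuous or ordinal) and compliance with the assumptions of normality with a confidence level of 95" percent. Neither the normality criterion nor the quantity it is applied to is named.

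Two effect sizes follow. The first is d, the mean of the Beetroot minus Placebo differences divided by s_d, with the definition "s_d = standard deviation of the differences". The second is r = Z/√n, introduced by "Thus, for the Wilcoxon test, the following was used", where "n = number of participants with data in both conditions". No interval is named for d, for r or for the mean difference, and no correction factor appears.

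The Human subjects protection review board section gives the sample: "44 people were required, but 10 were obtained". The Physical Tests section gives the outcomes in order, "beginning with a 40-meter sprint. After an adequate 10-minute rest period, the Bronco test is performed", and later the strength tests, "starting with the squat and then the bench press, and ending with the Borg scale".

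**The concern.** With about ten pairs, an effect size without an interval says little, and an exploratory analysis is useful mainly for its estimates and their uncertainty.

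The loss is uneven. Because d = t/√n, a reader given d and n can rebuild t and from it an interval for the standardized effect. From r and n the reader recovers only Z and a p-value. So a continuous outcome that the normality check sends to Wilcoxon loses any statement of how large the effect is, in test units or in SD units. It also cannot be set beside an outcome reported as d. Which outcomes end up this way depends on a check whose criterion is not stated.

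A lesser matter is that d, as written, is biased upward in small samples.

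**Working it through.** **Inputs.** n = 10 obtained and 44 required (Human subjects protection review board). The formulas for d and r come from the SAP. The number analysed is not stated, so n = 9 and n = 8 are shown as well. The 44 cannot be reproduced, because no effect size, SD, power or sidedness is given; this point does not depend on it.

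**1. Mean bias of d.** For normal, identically distributed differences with df = n - 1 and true standardized effect δ:

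E[d]/δ = √(df/2) · Γ((df-1)/2) / Γ(df/2)

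At n = 10: √4.5 · Γ(4)/Γ(4.5) = 2.1213 × 6/11.632 = 1.094. The usual correction is J = 1 - 3/(4·df - 1) = 1 - 3/35 = 0.914, and 1.094 × 0.914 = 1.000.

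| n | E[d]/δ | Mean bias | J |
|---|---|---|---|
| 8 | 1.126 | 12.6% | 0.889 |
| 9 | 1.108 | 10.8% | 0.903 |
| 10 | 1.094 | 9.4% | 0.914 |
| 44 | 1.018 | 1.8% | 0.982 |

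The median is less affected. At δ = 0.5 and n = 10, the median of d is 0.515 (3% high). After J it is 0.515 × 0.914 = 0.471 (6% low).

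**2. Sampling error of d.** With t = d√n, find the noncentrality values that put t at the 97.5% and 2.5% points of the noncentral t distribution, then divide by √n. For an observed d of 0.5:
- n = 10: -0.17 to 1.15, a width of about 1.3
- n = 9: -0.21 to 1.18
- n = 8: -0.25 to 1.22

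**3. Scale of r.** With 10 pairs, no ties and no continuity correction, the largest signed-rank sum is 55, its null mean is 27.5 and its null SD is √(10·11·21/24) = 9.81. The maximum Z is 27.5/9.81 = 2.80, so the maximum r is 2.80/√10 = 0.886. d has no upper limit. For the same normal data at n = 10, mean d and mean r are 0.55 and 0.44 at δ = 0.5, and 1.09 and 0.72 at δ = 1.0.

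**4. Does the remedy hold up without normality?** Simulation with n = 10, δ = 0.5, differences scaled to SD 1 and 200,000 samples per row. The shapes are assumptions.

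| Shape of differences | RMSE d → J·d | Mean J·d | Noncentral-t coverage | Raw mean t-interval coverage |
|---|---|---|---|---|
| Normal | 0.391 → 0.355 | 0.50 | 95% | 95% |
| t(3) | 0.483 → 0.427 | 0.63 | 92% | 96% |
| Exponential, tail against the effect | 0.783 → 0.702 | 0.70 | 82% | 90% |
| Exponential, tail with the effect | 0.269 → 0.247 | 0.47 | 98% | 90% |

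J lowers the error in every row but removes the bias only for normal differences. The interval for the raw mean difference is the steadier of the two, which is why it should be the main estimate.

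**5. Effect of a period shift.** Assume δ = 0.5, within-sequence SD 1, and a period shift of ±0.5 SD entering with opposite sign in the two sequence groups. Mean d is 0.48 with groups of 5 and 5 (J·d 0.44), and 0.69 with groups of 7 and 3 (J·d 0.63). J still lowers RMSE in both, but its near-unbiasedness needs the absence of a period effect as well as normality.

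**The case against.** The strongest reply is that nothing of consequence is at stake. The mean difference over the SD of the differences is a legitimate paired effect size, its bias is small beside its sampling error, and J moves the median from 3% high to 6% low. This stands as a limit on priority, and it means the formula should not be called wrong.

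Second, the 95% level may be meant to cover an interval for the mean difference, and a sentence introducing d may be lost from the extracted text. That d belongs to the t-test is itself inferred, from the contrast with the sentence introducing r. So a reader might infer that no interval at all will be reported; the visible text supports only that none is named for d or r.

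Third, a reader might infer that choosing the test by a normality check inflates the type I error, or that continuous outcomes ought to be moved from Wilcoxon to the t-test. Nothing in the documents shows the first. The second would be a trade-off and would change p-values in an analysis that the SAP describes in the past tense. Intervals can be added without it.

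Fourth, treating all four tests as continuous is an inference: the Physical Tests section does not say how squat and bench press are scored.

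**Conclusion.** The point holds as a low-priority reporting improvement. The SAP names no interval for either effect size, uses d without a small-sample factor, and leaves a continuous outcome judged non-normal with r alone. At n = 10 the mean bias of d is 9.4%, while the 95% interval around an observed 0.5 is about 1.3 wide, so the interval is the part that matters.

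These figures assume 10 analysed pairs and normal, identically distributed differences with no period effect. The ceiling of 0.886 on r assumes no ties. A reader might infer that the reported p-values or conclusions are unreliable on this account. The documents do not support that: the small-sample factor and the missing intervals leave every p-value as it is, and no conclusion is shown to alter.

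**What to change.** Add the following, leaving every test and p-value as it is.

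- **Every outcome scored on a continuous scale** (confirm this for squat and bench press): report the mean paired difference with its 95% CI as the main estimate, whatever the normality check says.
- **One standardized measure for those outcomes:** d × J, with J = 1 - 3/(4·df - 1) and the actual df (0.914 at n = 10), plus a noncentral-t 95% CI for the standardized effect. State that both assume normal, identically distributed differences with no period effect.
- **Borg, and any outcome tested by Wilcoxon:** keep r, add the Hodges-Lehmann difference with its CI, and state that r is not to be compared with d.
- **Disclosure:** because the SAP is in the past tense, describe these items as additions to the report.

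The cost is a few lines of text and code and no new data. Reported d falls by about 9% and becomes about 6% low in the median under normality. The t interval for the raw mean difference can fall to about 90% coverage when the differences are strongly skewed. The Hodges-Lehmann interval estimates its own target, which lies 0.16 SD from the mean for exponential differences, so it should not be presented as an interval for the mean.

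### Does leaving the Wilcoxon variant and the source of Z unstated require a change to the SAP?

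*Combined protocol and SAP*

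**What the plan says.** The Statistical Analysis Plan (SAP) names R as the software and labels the analysis descriptive and exploratory. Its rule for choosing a test is "Univariate tests were performed for the mean (paired Student t-test) or Wilcoxon depending on the type of variable (continuous or ordinal"), together with "compliance with the assumptions of normality with a confidence level of 95" per cent. For the paired t-test it gives d, the mean difference divided by the standard deviation of the differences (s_d). It then writes "Thus, for the Wilcoxon test, the following was used" and gives r = Z/√n, with "Z = Z statistics of the test" and "n = number of participants with data in both conditions".

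The SAP does not say which outcomes are ordinal. The Physical Tests section describes a sprint, the Bronco test and strength work, "starting with the squat and then the bench press, and ending with the Borg scale". Borg is the only rating scale among these, so it is presumably the ordinal outcome. On numbers, the section on the human subjects protection review board says "44 people were required, but 10 were obtained". The analysed n is not stated.

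**The concern.** Wilcoxon is not one procedure. The p-value can be exact or come from a normal approximation, the approximation can carry a continuity correction or not, and zero differences can be dropped or ranked. In large samples these choices hardly matter. With about 10 pairs of coarse ratings, where several differences are tied or zero, they can move p across 5%.

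Naming R does not fully close the gap. In R 4.3.3, wilcox.test returns V and p but no Z, so the r that the SAP promises needs a further step that the SAP does not describe. There is a second point: signed ranks discard the size of the change, so p and r cannot distinguish a one-point shift in Borg from a three-point shift. At stake are a verdict that depends on an undeclared choice and an effect size that cannot be read in Borg points.

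**Working it through.** **Inputs.** Ten pairs (the number of volunteers obtained, assumed complete). Two-sided 5% level (95% from the SAP; sidedness assumed). n in r counts all complete pairs, zeros included, as the SAP defines it. The documents give no Borg data, Borg version or SD, so all differences below are assumed. The plan has no figure of its own to reproduce on this point.

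**Formulas.** Drop zeros, leaving m pairs, and rank the absolute differences with mid-ranks. W+ has mean m(m+1)/4 and SD √(Σrank²/4). Z = (W+ − mean)/SD; the continuity correction moves W+ by 0.5 towards the mean. Exact p counts all 2^m sign patterns. r = Z/√10.

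**Case A: 7 one point lower, 1 one point higher, 2 equal.** m = 8, all ranks 4.5, W+ = 4.5, mean 18, SD √(8 × 20.25/4) = 6.364.
- Corrected (R default): Z = −13/6.364 = −2.043, p = 0.041, r = −0.65.
- Uncorrected: Z = −13.5/6.364 = −2.121, p = 0.034, r = −0.67.
- Exact: p = 2 × 9/256 = 0.070. This route has no Z of its own; converting p back gives −1.810 and r = −0.57.

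Tripling every difference leaves the ranks, and so all these figures, unchanged.

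**Case B: 5 one point lower, 5 equal.** m = 5, all ranks 3, W+ = 0, mean 7.5, SD √(5 × 9/4) = 3.354. Corrected Z = −7/3.354 = −2.087, p = 0.037. Uncorrected Z = −7.5/3.354 = −2.236, p = 0.025. Exact p = 2/32 = 0.0625.

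In A and B the two normal approximations agree at 5%, and only the exact route crosses.

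**Case C: differences −2, −2, −1, −1, −1 and five zeros.** Ranks 4.5 (twice) and 2 (three times), SD √(52.5/4) = 3.623. Corrected Z = −7/3.623 = −1.932, p = 0.053, r = −0.61. Uncorrected Z = −7.5/3.623 = −2.070, p = 0.038, r = −0.65. Here the continuity correction alone crosses 5%.

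**Untied differences, W+ = 8, m = 10.** Mean 27.5, SD √(385/4) = 9.811. Exact p = 0.049, corrected 0.053, uncorrected 0.047.

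**How often.** There are 8,007 possible sets of 10 integer differences from −3 to +3 that are not all zero. R default and exact disagree at 5% in 126 (126/8,007 = 1.6%). R default and uncorrected disagree in 168 (2.1%). These are counts of patterns, not probabilities.

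Simulations used rounded normal differences with SD 0.75 to 2 points and shifts of 0 or 0.5 to 1.0 SD:

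| Comparison at 5% | No shift | With shift |
|---|---|---|
| R default v exact | 0.4–1.8% | 1.5–11% |
| R default v uncorrected | about 1–2% | about 4–7% |
| Any of the three | 1.5–3.4% | 4.7–16% |

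**False positives with no shift.** R default 2.6–3.9%, exact 0.8–3.4%. Uncorrected reached 4.6% in one set of runs and 5.0% in another, so it sits at the nominal level. At SD 1 and a shift of 0.5 SD, power is 20.3% for R's default and 15.2% for exact.

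**t-test outcomes.** The 95% half-width is t(0.975, n−1)/√n times s_d: 2.262/3.162 = 0.715 at n = 10. The interval follows from the mean difference, s_d and n.

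**The case for a change.** The strongest argument for a change is that the choice really is open. The SAP names no R function, version or options. Base R supplies no Z. Case C shows that the continuity correction alone can decide the verdict. An analyst who has seen the data could pick whichever variant falls below 5%, and one sentence would prevent that at no cost in data. A rank effect size also leaves the reader unable to see how far the ratings moved.

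Much of this is true, but it carries little weight. The exact route fits the SAP poorly for tied ratings: it has no Z, and R 4.3.3 warns that it cannot compute an exact p and reports the corrected approximation instead. The exact-route r of −0.57 needs a back-conversion that the SAP does not describe. Between the two normal approximations r moves little (−0.65 to −0.67 in Case A, −0.61 to −0.65 in Case C). For untied continuous data the exact p is available, and in the example above it lies between the other two.

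That ranks lose the size of a change is true of any rank test. It does not show that the size will go unreported, because the SAP also plans a descriptive analysis, although it does not list the summaries. The SAP is written in the past tense, so a sentence added now might only record a choice already made.

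**Conclusion.** The gap is real but is one that an analyst fills sensibly. Following the SAP in R with tied ratings leads to the continuity-corrected normal approximation, whose simulated false-positive rate was 2.6–3.9%. The alternatives are also valid to within simulation error, and none is clearly better: the exact test gives up some power, and the uncorrected test uses the full 5%. Disagreements arise only near the threshold and in a minority of data sets. They affect outcomes sent to Wilcoxon, presumably Borg, since the sprint, Bronco, squat and bench press look continuous and go to the t-test unless normality fails.

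The analysis is labelled exploratory and no primary outcome is named, so no formal decision rests on a Borg p-value. Paired differences, counts of lower, equal and higher ratings, and intervals would help a reader of the results, but they are reporting additions that alter no test.

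This conclusion assumes 10 complete pairs, two-sided testing, rounded normal differences and the behaviour of R 4.3.3. The frequencies would shift with the actual Borg version and spread, which the documents do not give.
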